6.5.2 Cycle delay

The treatment window is ± 3 days for each of the Q3W administrations. A cycle is deemed to have been delayed if the treatment is administrated ≥ 4 days beyond the theoretical day of Q3W IMP administration. The participant may receive the next dose after recovery from the toxicity as described in [Section 6.5.3](#), and [Section 6.5.4](#). After cycle is delayed, such participants may be considered for treatment resumption once the toxicity resolves or improves to Grade 1 or baseline or is stable and manageable through supportive/medical therapy.

Participants may have cycle delay, if toxicity occurs and the participant does not recover according to following rules:

- For Q3W IMP administration: If toxicity occurs and the participant does not recover on the day of planned administration, the cycle will be delayed: restart of study IMPs could occur only on the initiation of the subsequent cycle.
- In case of cycle delay for the recovery of toxicity, the following rules should be followed for restart or discontinuation of the treatment:
 - In case of a cycle delay up to 14 days, it is per Investigator's decision to restart the study treatment.
 - After a cycle delay of >14 days and ≤ 84 days, it is per Investigator's decision to restart the study treatment, if a clear benefit from treatment is observed and after consultation with the Sponsor.
 - The study treatment must be permanently discontinued if the cycle delay is longer than 84 days.
- Cycle may be delayed for situations other than TEAEs such as medical / surgical events or logistical reasons not related to study therapy. Participants should be placed back on study therapy within 21 days of the scheduled delay, unless otherwise discussed with the Sponsor (for example for national or regional emergencies). The reason for this delay should be documented in the participant's study record.

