6.5.3 General guidelines for the management of treatment-related adverse events

Participants who experience Grade ≥ 3 treatment-related adverse events (TRAEs) at any time of the study (including clinically significant grade 3 laboratory abnormalities as defined in Section 10.3.1 of the master protocol) will be required to cycle delay the IMP, unless specified otherwise in the protocol, and with the exception of the TRAEs resolving within 5 days. After cycle delay, such participants may be considered for treatment resumption once the TRAE resolves or improves to Grade 1 or baseline or is stable and manageable through supportive/medical therapy. Treatment resumption is at the discretion of the Investigator and Sponsor, if thought to be in the best interest of the participant, except when specified otherwise in this protocol, or if the event has required the IMP temporary withheld for more than 84 days from the last scheduled dose.

The cycle delay of treatment for Grade 2 events is left at the discretion of the Investigator unless otherwise specified in this protocol.

No cycle delay of treatment or dose modification is required for Grade 1 events.

Dose reduction for SAR444245 from █ μg/kg to █ μg/kg (or another lower dose recommended by Study Board) may be decided when specified in the protocol or following discussions with the Sponsor.

The final decision on dose modification and/or corrective therapy will be based on the Investigator's judgment, in the best interest of the participant.

Recommended guidelines for the management of specific adverse events including irAE, CRS, vascular leak syndrome (VLS) and IRR are presented in [Section 6.5.4](#).

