- If the toxicities do resolve and conditions are aligned with what is defined in [Table 6](#), the combination of SAR444245 and pembrolizumab may be restarted at the discretion of the Investigator. In these cases where the toxicity is attributed to the combination or to SAR444245 alone, re-initiation of pembrolizumab as a monotherapy may be considered after communication with the Sponsor.

Table 6 - Dose modification and toxicity management guidelines for immune-related AEs associated with pembrolizumab and SAR444245

General instructions:

1. Severe and life-threatening irAEs should be treated with IV corticosteroids followed by oral steroids. Other immunosuppressive treatment should begin if the irAEs are not controlled by corticosteroids.
2. Pembrolizumab and SAR444245 must be permanently discontinued if the irAE does not resolve or the corticosteroid dose is not \leq 10 mg/day within 12 weeks of the last pembrolizumab treatment.
3. The corticosteroid taper should begin when the irAE is \leq Grade 1 and continue at least 4 weeks.
4. If pembrolizumab and SAR444245 have been withheld, pembrolizumab and SAR444245 may be resumed after the irAE decreased to \leq Grade 1 after corticosteroid taper.

irAEs	Toxicity grade (CTCAE V5.0)	Action with pembrolizumab and SAR444245	Corticosteroid and/or other therapies	Monitoring and follow-up
Pneumonitis	Grade 2	Withhold ^a	Administer corticosteroids (initial dose of 1 - 2 mg/kg prednisone or equivalent) followed by taper.	Monitor participants for signs and symptoms of pneumonitis.
	Recurrent Grade 2, Grade 3 or 4	Permanently discontinue ^b	Add prophylactic antibiotics for opportunistic infections.	Evaluate participants with suspected pneumonitis with radiographic imaging and initiate corticosteroid treatment.

irAEs	Toxicity grade (CTCAE V5.0)	Action with pembrolizumab and SAR444245	Corticosteroid and/or other therapies	Monitoring and follow-up
Diarrhea/Colitis	Grade 2 or 3	Withhold ^a	Administer corticosteroids (initial dose of 1 - 2 mg/kg prednisone or equivalent) followed by taper.	Monitor participants for signs and symptoms of enterocolitis (ie, diarrhea, abdominal pain, blood or mucus in stool with or without fever) and of bowel perforation (ie, peritoneal signs and ileus). Participants with ≥Grade 2 diarrhea suspecting colitis should consider GI consultation and performing endoscopy to rule out colitis.

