6.5.2 Dose delay and dose omission

Within a cycle, the treatment windows are:

- For the Q2W administration, the C_{n+1} (± 2 days), dose is deemed to have been delayed if the treatment is ≥ 3 days beyond the theoretical day of treatment.
- The reason for the dose delay will be captured. If the reason for the dose delay is an adverse event, the participant will receive the next infusion after recovery of the AE as described in [Section 6.5.2](#) and [Section 6.5.3](#)

Participants may have dose omission if an AE occurs and does not recover according to following rules:

- If an AE occurs and the participant does not recover on the day of planned infusion or within the following 2 days, infusion of SAR444245 may be omitted for participants.
- In case of consecutive dose omissions/delay for the recovery of AE, the following rules should be followed for restart or discontinuation of the treatment:
 - Dose delay (cycle delay) up to 9 days, it is per Investigator's decision to restart the study treatment.
 - After dose delay of >9 days and ≤ 84 days, it is per Investigator's decision to restart the study treatment, if a clear benefit from treatment is observed and after consultation with the Sponsor.
 - Treatment must be permanently discontinued if the delay is longer than 84 days.

Cycle may be delayed for situations other than TEAEs such as medical / surgical events or logistical reasons not related to study therapy. Participants should be placed back on study therapy within 14 days of the scheduled delay, unless otherwise discussed with the Sponsor (for example for national or regional emergencies). The reason for this delay should be documented in the participant's study record.

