3.6.1 Extent of exposure

If applicable, summaries will be provided by trial impact (disruption) due to COVID-19.

3.6.1.1 *Overall exposure*

The dose information will be assessed by the following variables:

- Overall number of cycles started, defined by the number of cycles in which at least one dose of any study interventions is administered.
- Duration of IMP exposure (in months) is defined as (Last day of exposure – first day of exposure +1)/30.4375.
- The first day of exposure is defined as the first administration date with non-zero dose for at least one of the IMP (SAR444245 or pembrolizumab).

The last day of exposure is the day before the theoretical date of the next administration (after the last administration), defined as the maximum between:

For cohort A

- The last administration date + 20 days for SAR444245
- The last administration date + 20 days for pembrolizumab

For cohort C1

- The last administration date + 13 days for SAR444245

The total number of cycles started, and number of cycles started by participants will be summarized by category.

The duration of overall exposure will be summarized quantitatively.

The following variable will be computed to describe overall dose modification (cycle delay):

- Cycle delay: A cycle is deemed as delayed if the start date of the current cycle – theoretical duration of a cycle – start date of the previous cycle is \geq 4 days (in cohort A); \geq 3 days in cohort C1. Cycle delay is not defined for the first cycle.

Cycle delay will be analyzed at the participant (with number of participants used as denominator) and cycle (with number of cycles used as denominator) levels, as follows:

- Number (%) of participants with at least 1 cycle delayed
 - Number (%) of participants with a cycle delayed between 4 and 7 days (using maximum delay across all cycles)
 - Number (%) of participants with a cycle delayed $>$ more than 7 days (using maximum delay across all cycles)
- Number (%) of cycles delayed
 - Number (%) of cycles delayed between 4 and 7 days
 - Number (%) of cycles delayed $>$ more than 7 days

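### Substudy 01 counts the 84-day (12-week) stopping limit from different dates, so an immune-related event that recovers between days 85 and 105 must stop under Table 6 but may restart under Section 6.5.2

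*Protocol*

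**What the plan says.** **Substudy 01, Section 6.5.2 (Cycle delay).** Delay is measured from the day on which the next dose was due: "A cycle is deemed to have been delayed if the treatment is administrated ≥ 4 days beyond the theoretical day of Q3W IMP administration". Restart stays open for a long delay: "After a cycle delay of >14 days and ≤ 84 days, it is per Investigator's decision to restart the study treatment", on condition that benefit is clear and the Sponsor has been consulted. Beyond that, "The study treatment must be permanently discontinued if the cycle delay is longer than 84 days". The section refers to 6.5.3 and 6.5.4 for what counts as recovery.

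**Substudy 01, Section 6.5.4.4, Table 6 (irAEs), general instruction 2.** "Pembrolizumab and SAR444245 must be permanently discontinued if the irAE does not resolve", and the same sentence adds a second condition, that the corticosteroid dose be at or below "10 mg/day within 12 weeks of the last pembrolizumab treatment". Footnote a of the table treats withholding both drugs as a cycle delay.

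**Substudy 01, Section 6.5.3 (treatment-related adverse events in general).** Resumption is at the discretion of the Investigator and Sponsor, except where the protocol specifies otherwise, or "if the event has required the IMP temporary withheld for more than 84 days from the last scheduled dose".

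**Substudy 03.** Section 6.5.2 has the same length of limit: "Treatment must be permanently discontinued if the delay is longer than 84 days". Section 6.5.3 repeats the Substudy 01 wording on the last scheduled dose. There is no irAE table.

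**SAP, Section 3.6.1.** The derivation of delay follows 6.5.2: "A cycle is deemed as delayed if the start date of the current cycle – theoretical duration of a cycle – start date of the previous cycle" must reach 4 days in Cohort A or 3 days in Cohort C1.

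**The concern.** The limits look the same because 84 days and 12 weeks are equal in length, but their starting dates differ. One starts when a dose is missed. Another starts when pembrolizumab was last given, normally a full cycle earlier. The starting date of the third depends on how a phrase is read.

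These are mandatory stopping rules, so sites that follow different passages could re-dose one participant and permanently stop another with the same course. The choice also feeds planned SAP outputs: events leading to permanent full discontinuation (Table 8), reasons for discontinuation (Appendix 2), and exposure and dose intensity (Section 3.6.1). With 25 participants in a cohort, one reclassified participant moves a percentage by 1/25 = 4 points.

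**Working it through.** The plan states the limits but no interval between them, so there is no published figure to reproduce. The check is calendar arithmetic. Day 0 is the last Day 1 on which both drugs were given.

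**Inputs**
- Cycle length: 21 days in Cohort A and 14 days in Cohort C1 (footnote b of each schedule of activities).
- Limit in 6.5.2: 84 days of cycle delay.
- Limit in Table 6: 12 weeks from the last pembrolizumab treatment.
- Limit in 6.5.3: 84 days from the last scheduled dose.

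**Cohort A**
1. Lengths: 12 × 7 = 84 days. The lengths agree, so only the start points differ.
2. Section 6.5.2: by the SAP formula, a restart on day *d* has a delay of *d* − 21 − 0. Setting this to 84 gives *d* = 21 + 84 = **day 105**.
3. Table 6: 12 × 7 = **day 84**.
4. Gap: 105 − 84 = **21 days**, that is days 85 to 105. The corresponding cycle delays are 85 − 21 = 64 days to 105 − 21 = 84 days, all inside the band where 6.5.2 permits restart.
5. Do both rules apply to one participant? Yes. Footnote a makes withholding both drugs for an irAE a cycle delay, and the 84-day bullets in 6.5.2 contain no irAE exception.
6. Example of conflict: an irAE that resolves only on day 95. The delay is 95 − 21 = 74 days, which is above 14 and not above 84, so 6.5.2 permits restart with clear benefit and Sponsor consultation. Table 6 has already required permanent discontinuation, because the irAE was unresolved at day 84.
7. Example without conflict: an irAE that has resolved by day 84 with corticosteroids at or below 10 mg/day by then, and dosing restarted on day 95. Neither rule is broken.
8. Sensitivity: if the theoretical day is held on a fixed grid, the ±3-day window puts the next due date 18 to 24 days after the last dose. The gap is then 18 + 84 − 84 = 18 days to 24 + 84 − 84 = 24 days.

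**The wording of 6.5.3**

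| Reading of *last scheduled dose* | Cohort A | Cohort C1 |
|---|---|---|
| The missed dose | 21 + 84 = day 105 | 14 + 84 = day 98 |
| The last dose given | day 84 | day 84 |
| Difference | 21 days | 14 days |
| Limit in 6.5.2 | day 105 | day 98 |

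On the first reading, 6.5.3 agrees with 6.5.2 in both substudies. On the second, it falls one cycle earlier. On either reading, Cohort A has only two distinct calendar limits, days 84 and 105.

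**The case against.** The strongest reply is that the rules already have an order. Section 6.5.2 refers to 6.5.4 for recovery. Section 6.5.3 gives way to whatever is specified elsewhere in the protocol. Section 6.5.4.4 requires all study drugs to stop when the criteria for resuming are not met, and ties restart to the conditions of Table 6. On this view 6.5.2 is an outer limit for any toxicity and Table 6 a narrower rule for irAEs. Because 6.5.2 only permits restart, a site that stops under Table 6 breaches nothing.

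Much of this stands. The cross-references do suggest that Table 6 is meant to govern irAEs. But the restart and stop bullets in 6.5.2 make no exception for irAEs, and no sentence gives Table 6 precedence. A site that applies 6.5.2 as written can restart a participant whom Table 6 requires to stop. The rule to follow the most conservative recommendation does not settle it either: 6.5.1 states it for several toxicities and 6.5.4.4 for several irAEs, not for one event under two rules.

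A second reply concerns impact. Every restart in the 21-day interval needs Sponsor consultation, since a delay of 64 to 84 days exceeds 14. The SAP also derives cycle delay by one formula whichever passage a site follows. Both points stand, and they limit how far sites could diverge. They do not tell the Sponsor or the site which passage applies.

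**Conclusion.** The conflict in Substudy 01 is real but confined. It arises for an irAE that first meets the Table 6 conditions (resolved, and corticosteroids at or below 10 mg/day) between days 85 and 105 after the last dose. The 21-day figure assumes that both drugs were last given on the same day and that the due date is 21 days later, as in the SAP formula. The documents give no basis for estimating how many participants this would affect.

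A reader might infer three stronger points that the documents do not support:
- **Three separate limits.** Three start points are worded, but when both drugs were last given together they yield only two calendar limits. *Last scheduled dose* coincides with either the missed dose or the last dose given.
- **A clash for every participant delayed into days 85 to 105.** An irAE that met both Table 6 conditions by day 84 is not in conflict. For other treatment-related events, a clash exists only if *last scheduled dose* means the last dose given.
- **The same contradiction in Substudy 03.** That substudy has no counterpart to Table 6. It has an undefined phrase, which may or may not put 6.5.3 up to 14 days ahead of 6.5.2. This is an ambiguity, not a demonstrated contradiction.

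**What to change.** Reconcile Sections 6.5.2, 6.5.3 and Table 6 (instruction 2) in Substudy 01, and Sections 6.5.2 and 6.5.3 in Substudy 03:
1. Name the reference date from which each limit is counted.
2. Define *last scheduled dose* in 6.5.3 of both substudies as either the missed dose or the last dose given.
3. State in 6.5.2 of Substudy 01 which passage prevails for irAEs.

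The sponsor's clinical team must choose the limit and the start date; this review takes no view on either. The cost is protocol wording only.

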6.5.3 General guidelines for the management of treatment-related adverse events

Participants who experience Grade ≥ 3 treatment-related adverse events (TRAEs) at any time of the study (including clinically significant grade 3 laboratory abnormalities as defined in Section 10.3.1 of the master protocol) will be required to cycle delay the IMP, unless specified otherwise in the protocol, and with the exception of the TRAEs resolving within 5 days. After cycle delay, such participants may be considered for treatment resumption once the TRAE resolves or improves to Grade 1 or baseline or is stable and manageable through supportive/medical therapy. Treatment resumption is at the discretion of the Investigator and Sponsor, if thought to be in the best interest of the participant, except when specified otherwise in this protocol, or if the event has required the IMP temporary withheld for more than 84 days from the last scheduled dose.

The cycle delay of treatment for Grade 2 events is left at the discretion of the Investigator unless otherwise specified in this protocol.

No cycle delay of treatment or dose modification is required for Grade 1 events.

Dose reduction for SAR444245 from █ μg/kg to █ μg/kg (or another lower dose recommended by Study Board) may be decided when specified in the protocol or following discussions with the Sponsor.

The final decision on dose modification and/or corrective therapy will be based on the Investigator's judgment, in the best interest of the participant.

Recommended guidelines for the management of specific adverse events including irAE, CRS, vascular leak syndrome (VLS) and IRR are presented in [Section 6.5.4](#).

6.5.4 Guidelines for the management of specific adverse events

Specific adverse events described in sections below may classify as adverse events of special interests (AESIs), depending on grading according to National Cancer Institute- Common Terminology Criteria for Adverse Event (NCI-CTCAE) V5.0 (see Section 8.3.8 of the master protocol). In case a specific adverse event meets the AESI definition it must be documented in the electronic case report form (e-CRF).

6.5.4.1 Infusion-related reactions (IRR)

Participants should routinely receive premedication as detailed in Section 6.1.2.1 of the master protocol, prior to SAR444245 administration, to prevent or reduce the incidence or severity of IRRs.

An infusion-related reaction (IRR) in this study is defined as any signs or symptoms which develop during the infusion or up to 24 hours after the completion of the infusion. The term IRR indicates only a specific temporal relationship with the infusion and does not specify a particular mechanism underlying the signs or symptoms.

Pembrolizumab may cause severe or life-threatening infusion-reactions including severe hypersensitivity or anaphylaxis. Signs and symptoms usually develop during or shortly after drug

infusion and generally resolve completely within 24 hours of completion of infusion. Dose modification and toxicity management guidelines on pembrolizumab-associated infusion reaction are provided in [Table 3](#).

After an IRR due to pembrolizumab infusion (Grade 3 or Grade 4), the SAR444245 infusion will be delayed and can be administered after resolution of symptoms. The Investigator should discuss with the Sponsor's Medical Monitor if the SAR444245 infusion needs to be delayed more than 1 day.

Guidelines for the management of SAR444245 IRR events are provided in [Table 4](#). Participants who develop Grade 2 IRR should have the next SAR444245 infusion given at half the infusion rate. For instructions on premedication at subsequent dosing, please see Section 6.1.2.1 of the master protocol.

Table 3 - Pembrolizumab infusion-related reaction dose modification and treatment guidelines

NCI CTCAE Grade	Treatment	Premedication at subsequent dosing
Grade 1 Mild reaction; infusion interruption not indicated; intervention not indicated	
 Increase monitoring of vital signs as medically indicated until the participant is deemed medically stable in the opinion of the investigator. 	None
Grade 2 Requires therapy or infusion interruption but responds promptly to symptomatic treatment (eg, antihistamines, NSAIDs, narcotics, IV fluids); prophylactic medications indicated for ≤24 hrs.	
 Stop Infusion. Additional appropriate medical therapy may include but is not limited to: 
 - IV fluids, - Antihistamines, - NSAIDs, - Acetaminophen, - Narcotics. Increase monitoring of vital signs as medically indicated until the participant is deemed medically stable in the opinion of the investigator. If symptoms resolve within 1 hour of stopping drug infusion, the infusion may be restarted at 50% of the original infusion rate (eg, from 100 mL/hr. to 50 mL/hr.). Otherwise dosing will be held until symptoms resolve and the participant should be premedicated for the next scheduled dose. 	Participant may be premedicated 1.5 h (±30 minutes) prior to infusion of pembrolizumab with: Diphenhydramine 50 mg po (or equivalent dose of antihistamine). Acetaminophen 500-1000 mg po (or equivalent dose of analgesic).
Participants who develop Grade 2 toxicity despite adequate premedication should be permanently discontinued from further study drug treatment		
Grades 3 or 4	
 Stop Infusion. 	No subsequent dosing
Grade 3: Prolonged (ie, not rapidly responsive to symptomatic medication and/or brief interruption of infusion); recurrence of symptoms	
 Additional appropriate medical therapy may include but is not limited to: 
 - Epinephrine*, - IV fluids, - Antihistamines, - NSAIDs, 	

NCI CTCAE Grade	Treatment	Premedication at subsequent dosing
following initial improvement; hospitalization indicated for other clinical sequelae (eg, renal impairment, pulmonary infiltrates)	
 - Acetaminophen, - Narcotics, - Oxygen, - Pressors, - Corticosteroids. 	
Grade 4: Life-threatening; pressor or ventilator support indicated	
 • Increase monitoring of vital signs as medically indicated until the participant is deemed medically stable in the opinion of the investigator. • Hospitalization may be indicated. 
*In cases of anaphylaxis, epinephrine should be used immediately.
 
Participant is permanently discontinued from further study drug treatment.
	

Appropriate resuscitation equipment should be available at the bedside and a physician readily available during the period of drug administration. For further information, please refer to the Common Terminology Criteria for Adverse Events v5.0 (CTCAE) at <http://ctep.cancer.gov>.

Table 4 - SAR444245 Infusion-related reaction dose modification and treatment guidelines

NCI CTCAE Grade	Treatment
Grade 1 Mild reaction; infusion interruption not indicated; intervention not indicated	
If IRR happens during infusion, continuation of SAR444245^a infusion is per Investigator's judgment following close direct monitoring of the participant's clinical status.
 
SAR444245 infusion may be interrupted at any time if deemed necessary.
 
If interrupted, IRR will be classified as Grade 2 as per NCI-CTCAE definition.
 
If IRR happens after completion of infusion, increase monitoring of vital signs as medically indicated until the participant is deemed medically stable in the opinion of the investigator.

Grade 2 Requires therapy or infusion interruption but responds promptly to symptomatic treatment (eg, antihistamines, NSAIDs, narcotics, IV fluids); prophylactic medications indicated for ≤24 hrs.	
SAR444245 infusion should be interrupted if applicable.
 
If symptoms resolve within 1 hour of interrupting drug infusion, the infusion may be restarted at 50% of the original infusion rate. Otherwise, dosing will be held until symptoms resolve and the participant should be premedicated for the next scheduled dose according to Section 6.1.2.1 of the master protocol.
 
The next infusion should be given at half the infusion rate.
 
During or after completion of infusion, additional appropriate medical therapy may include but not limited to IV fluids, antihistamines, NSAIDs, acetaminophen, narcotics.
 
Increase monitoring of vital signs will be as medically indicated until the participant recovers.

Grade 3	SAR444245 infusion should be interrupted if applicable. If IRR is clearly attributable to SAR444245, SAR444245 should be permanently discontinued. The participant can continue treatment with the other anti-cancer therapy in combination. During or after completion of infusion, additional appropriate medical therapy may include but is not limited to epinephrine ^b , IV fluids, antihistamines, NSAIDs, acetaminophen, narcotics, oxygen, vasopressors, corticosteroids. Increase monitoring of vital signs as medically indicated until the participant recovers.
Grade 4	SAR444245 infusion should be interrupted if applicable. If IRR is clearly attributable to SAR444245, SAR444245 should be permanently discontinued. The participant can continue treatment with the other anti-cancer therapy in combination. During or after completion of infusion, additional appropriate medical therapy may include but is not limited to epinephrine ^b , IV fluids, antihistamines, NSAIDs, acetaminophen, narcotics, oxygen, vasopressors, corticosteroids. Increase monitoring of vital signs as medically indicated until the participant recovers.

a Information for preparation and storage of SAR444245 is provided in the pharmacy manual.

b In cases of anaphylaxis, epinephrine should be used immediately

Abbreviations: CTCAE = Common terminology criteria for adverse events; IRR = Infusion related reaction; NCI = National Cancer Institute; NSAIDs: nonsteroidal anti-inflammatory drugs.

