6.5 DOSE MODIFICATION

6.5.1 General rules

Dose modification for SAR444245 is permitted according to the guidelines described in this section. Pembrolizumab dose reductions are not permitted. Pembrolizumab treatment may be withheld or discontinued due to toxicity.

Dose modifications different from those stated in the protocol should only be made in consultation with the Sponsor, unless required for immediate participant safety.

Cycle delay (ie, Day 1 should be delayed for all IMPs) is permitted in case of treatment-emergent adverse event (TEAE). Dose modification will be made according to the worst grade of toxicity observed within a cycle. If a participant experiences several toxicities and there are conflicting recommendations, the most conservative recommended dose adjustment should be followed. Once a dose has been decreased, intra-patient re-escalation back to the previous dose level is not permitted.

Administration of the study treatment will be discontinued in the event of a TEAE that persists despite appropriate dose modifications or any other TEAE that, in the opinion of the Investigator, warrants discontinuation.

If any of the IMP components is permanently discontinued, the other IMP component can be continued until disease progression or other criteria as detailed in Section 7.1.1 of the master protocol are met. In this case it is partial permanent discontinuation and the end of treatment (EOT) assessment will be 30 days after the date of the last administration of the remaining IMP. When all IMP components are permanently discontinued it is full permanent discontinuation.

All changes to study treatment administration must be recorded in the electronic case report form (e-CRF).

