6.5.4.2 Anaphylaxis

Anaphylaxis should lead to immediate interruption of ongoing infusion, and to permanent discontinuation of both SAR444245 and pembrolizumab being administered.

Management should be prompt and may include but is not limited to administration of epinephrine, IV fluids, antihistamines, oxygen, vasopressors, corticosteroids, as well as increased monitoring of vital signs as medically indicated, until the participant recovers (see guidelines) (26, 27, 28).

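### Substudy 01 gives opposite instructions for SAR444245 when a pembrolizumab infusion reaction is anaphylaxis, and Table 3 does not name the drug it permanently stops

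*Protocol*

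**What the plan says.** Cohort A has two IMPs, SAR444245 and pembrolizumab (Substudy 01, Section 6.1.1). Five places in Substudy 01 bear on what happens to SAR444245 after an infusion reaction.

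- **Section 6.5.4.1, running text.** Anaphylaxis is listed among the reactions pembrolizumab may cause. After a Grade 3 or 4 pembrolizumab reaction, "the SAR444245 infusion will be delayed and can be administered after resolution of symptoms". A discussion with the Medical Monitor is asked for "if the SAR444245 infusion needs to be delayed more than 1 day". Anaphylaxis is not excepted.
- **Table 3.** The title is "Table 3 - Pembrolizumab infusion-related reaction dose modification and treatment guidelines". The Grade 3 or 4 row says "Participant is permanently discontinued from further study drug treatment", with "No subsequent dosing" in the premedication column. The same row carries a note on immediate epinephrine in anaphylaxis. The Grade 2 row says "Participants who develop Grade 2 toxicity despite adequate premedication should be permanently discontinued from further study drug treatment". Neither row names the drug.
- **Table 4 (SAR444245 reactions).** For Grades 3 and 4 it names SAR444245 as the drug to be stopped if the reaction is clearly attributable to it, and adds that the combination partner can go on.
- **Section 6.5.4.2.** Anaphylaxis leads "to permanent discontinuation of both SAR444245 and pembrolizumab being administered".
- **Section 6.5.1.** "If any of the IMP components is permanently discontinued, the other IMP component can be continued", until progression or another stopping criterion. This is called partial permanent discontinuation, and EOT is then set 30 days after the last dose of the remaining IMP. Stopping all IMPs is full permanent discontinuation.

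SAP Section 5.2 defines partial and full discontinuation on the same basis and uses study drugs to cover both SAR444245 and pembrolizumab.

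**The concern.** A site managing a severe pembrolizumab reaction would look to Section 6.5.4.1 and Table 3 first. If the reaction is anaphylaxis, the running text there allows SAR444245 later, while the next section permanently stops it. If the reaction is severe but not anaphylaxis, the running text allows SAR444245, while Table 3 can be read as stopping everything.

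Two things are at stake. The first is that sites may act differently on the same, potentially life-threatening event. The second is reporting. Whether SAR444245 continues determines whether the participant is a full or a partial permanent discontinuation, which SAP Table 8 and SAP Section 5.2 report separately. It also fixes when the EOT visit falls and how long adverse events count as treatment-emergent. If sites read the text differently, those tables will partly reflect site interpretation.

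**Working it through.** The plan gives no figure to reproduce. The check sets the instructions for SAR444245 side by side, reading Table 3 first as pembrolizumab only and then as both drugs.

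| Event | 6.5.4.1 text | Table 3 as pembrolizumab only | Table 3 as both drugs | 6.5.1 | 6.5.4.2 |
|---|---|---|---|---|---|
| Grade 3-4 pembrolizumab reaction that is anaphylaxis | delay, then may be given | silent on SAR444245 | stop | may continue | stop |
| Grade 3-4 pembrolizumab reaction, not anaphylaxis | delay, then may be given | silent on SAR444245 | stop | may continue | does not apply |
| Grade 2 despite premedication | no sentence on SAR444245 | silent on SAR444245 | stop | may continue | does not apply |

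**Row 1.** Section 6.5.4.1 and Section 6.5.4.2 disagree however Table 3 is read. Section 6.5.1 does contain a rule to follow the most conservative recommendation, but it is written for a participant with several toxicities, not for one event covered by two sections. No other precedence is stated.

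**Row 2.** There is a conflict only if Table 3 means both drugs.
- For pembrolizumab only: the table title; the premedication column, which concerns pembrolizumab infusions; the specific SAR444245 sentence in Section 6.5.4.1; and Section 6.5.1. Where both drugs are meant, the substudy says so elsewhere: Section 6.5.4.2 names both, Section 6.5.4.4 refers to all study drugs, and footnote b of Table 6 refers to full study treatment.
- For both drugs: both are IMPs in Cohort A, the SAP uses study drugs for both, and Table 3 has no counterpart to the continuation sentence in Table 4.

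**Row 3.** No SAR444245-specific sentence contradicts Table 3. Only the permissive Section 6.5.1 does, so this is an unnamed drug rather than a direct conflict.

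**Effect on reporting.** Let L be the date of the last IMP dose.
- The on-treatment period ends at L + 30 days (Master Protocol Section 9.4.1; SAP Section 3.1), and the EOT visit is nominally at L + 30 days.
- Overall exposure in Cohort A ends at the later of the two drugs' last dose + 20 days (SAP Section 3.6.1.1).
- If SAR444245 continues for k further undelayed 21-day cycles, L moves by 21 × k days, and all three dates move with it. As an illustration, k = 3 gives 21 × 3 = 63 days.
- SAP Table 8 reports adverse events leading to partial discontinuation for each individual drug, so pembrolizumab stopped alone can be shown there. The Cohort A disposition list in SAP Section 5.2 has a partial-discontinuation row only for stopping SAR444245, so pembrolizumab stopped with SAR444245 continued has no row.

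**Effect on the primary endpoint.** SAP Section 3.2.2 handles early IMP discontinuation by treatment policy. The efficacy population and the rule for which tumor assessments count do not depend on the full or partial label.

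**The case against.** The strongest reply is that, read in context, the sections mostly agree. Table 3 is a pembrolizumab table, SAR444245 has its own sentence for the Grade 3-4 event, Section 6.5.1 provides for continuing one drug, and full stops are spelled out elsewhere. Reading Table 3 as stopping both drugs would leave the SAR444245 sentence in Section 6.5.4.1 with no effect. Anaphylaxis has its own heading, so at most a cross-reference is missing. The SAP classifies by what was actually stopped, so the derivation is defined however sites act.

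Much of this stands. A reader might infer any of the following, and the documents do not support them:
- That continuation of SAR444245 is wholly undecided after every Grade 3-4 reaction. For non-anaphylactic reactions the pembrolizumab-only reading is the better supported one.
- That every such event has three competing written actions. Section 6.5.4.2 applies only to anaphylaxis.
- That Grade 2 despite premedication is the same contradiction. It has no SAR444245-specific text to conflict with.
- That the plan allows re-exposure to the offending drug within about a day. The drug at issue is SAR444245, and one day is the point beyond which a discussion is required, not a re-dosing deadline.

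The reply does not remove the anaphylaxis conflict, because Section 6.5.4.1 itself brings anaphylaxis within pembrolizumab reactions and then makes no exception for it. It also does not explain why Table 4 names the drug and Table 3 does not. Section 6.5.1 is permissive and does not say whether it or Table 3 governs.

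**Conclusion.** The point holds in two parts of unequal strength. For anaphylaxis due to pembrolizumab, Sections 6.5.4.1 and 6.5.4.2 give opposite instructions for SAR444245 under any reading of Table 3. For other Grade 3-4 reactions, and for Grade 2 despite premedication, Table 3 leaves the drug unnamed. The likely meaning is pembrolizumab only, but a literal reader could stop both drugs.

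The consequence is the full or partial classification and the dates of the EOT visit, the TEAE window and overall exposure. The rule for the primary complete response rate is unchanged.

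The number of participants affected cannot be estimated, because the documents give no frequency for these reactions by grade. Two figures could be mistaken for a size. Up to 35 - 1 = 34 further cycles requires a Cycle 1 reaction followed by treatment to the maximum. The value 1/25 = 4 percentage points is only what one participant contributes to a rate at N = 25. Neither measures likely impact.

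One limit applies: the Cohort A dosing sequence is redacted, so any instruction given there cannot be seen.

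**What to change.** Reconcile Substudy 01 Sections 6.5.1, 6.5.4.1 (text and Table 3) and 6.5.4.2:

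- In each Table 3 discontinuation row (Grade 2 despite premedication, and Grades 3 or 4), name the IMP or IMPs permanently stopped and say whether the other may continue.
- In Section 6.5.4.1, state how the SAR444245 sentence relates to the anaphylaxis rule in Section 6.5.4.2.
- If stopping pembrolizumab while continuing SAR444245 is allowed, add the matching Cohort A partial-discontinuation row to SAP Section 5.2.

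Which drugs stop, and when, is the sponsor's clinical decision. The cost is a few sentences in the substudy protocol and one row in the SAP. Sample size, data collection and the primary analysis are untouched.
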